15.2 Randomization

Not applicable.

16.0 DATA MANAGEMENT ISSUES

A Research Study Assistant (RSA) will be assigned to the study. The responsibilities of the RSA include project compliance, data collection, abstraction and entry, data reporting, regulatory monitoring, problem resolution and prioritization, and coordinate the activities of the protocol study team. The data collected for this study will be entered into a secure database. Source documentation will be available to support the computerized patient record.

16.1 Quality Assurance

Weekly registration reports will be generated to monitor patient accruals and completeness of registration data. Routine data quality reports will be generated to assess missing data and inconsistencies. Accrual rates and extent and accuracy of evaluations and follow-up will be monitored periodically throughout the study period and potential problems will be brought to the attention of the study team for discussion and action. Random-sample data quality and protocol compliance audits will be conducted by the study team, at a minimum of two times per year, more frequently if indicated.

16.2 Data and Safety Monitoring

The Data and Safety Monitoring (DSM) Plans at Memorial Sloan-Kettering Cancer Center were approved by the National Cancer Institute in September 2001. The plans address the new policies set forth by the NCI in the document entitled “Policy of the National Cancer Institute for Data and Safety Monitoring of Clinical Trials” which can be found at: <http://cancertrials.nci.nih.gov/researchers/dsm/index.html>. The DSM Plans at MSKCC were established and are monitored by the Office of Clinical Research. The MSKCC Data and

Safety Monitoring Plans can be found on the MSKCC Intranet at:
<http://mskweb5.mskcc.org/intranet/assets/tables/content/359709/DSMPlans07.pdf>

There are several different mechanisms by which clinical trials are monitored for data, safety and quality. There are institutional processes in place for quality assurance (e.g., protocol monitoring, compliance and data verification audits, therapeutic response, and staff education on clinical research QA) and departmental procedures for quality control, plus there are two institutional committees that are responsible for monitoring the activities of our clinical trials programs. The committees: *Data and Safety Monitoring Committee (DSMC)* for Phase I and II clinical trials, and the *Data and Safety Monitoring Board (DSMB)* for Phase III clinical trials, report to the Center's Research Council and Institutional Review Board.

During the protocol development and review process, each protocol will be assessed for its level of risk and degree of monitoring required. Every type of protocol (e.g., NIH sponsored, in-house sponsored, industrial sponsored, NCI cooperative group, etc.) Will be addressed and the monitoring procedures will be established at the time of protocol activation.

17.0 PROTECTION OF HUMAN SUBJECTS

Participation in the research study is voluntary. The patients will be explained the risk, benefits, toxicities/side effects, treatment alternatives/options, financial costs/burdens and the voluntary nature of the study. Informed consent will be obtained as detailed in section 18.0.

Benefits: It is possible that treatment with dabrafenib will result in improved relapse-free survival. This could lead to improvement in overall survival.

Costs: Dabrafenib is an investigational drug that will be provided by Novartis to all study participants. Costs for venipuncture for research bloods will not be billed to the patient unless part of by clinical blood test venipuncture. All other standard medical costs will be the responsibility of the study participants. Biopsies performed at progression of disease are a standard of care and will be billed to the patient. Research testing on the tissue will not be charged to the subject. BRAF testing, if not done prior to enrollment, performed to determine subject eligibility will not be billed to the patient.

Incentives: No incentives will be provided to participants in the trial.

Alternatives: Other treatment options are available for patients with stage IIIC melanoma who choose not to participate in this investigational study. Other alternatives include participation in another clinical trial, adjuvant high dose or pegylated interferon, adjuvant radiotherapy, or expectant observation.

Confidentiality: All research and medical records are confidential in accordance with Health Insurance Portability and Accountability Act. Protected information will not be released or reported in any presentations or publications that may result from this study.

17.1 Privacy

MSKCC's Privacy Office may allow the use and disclosure of protected health information pursuant to a completed and signed Research Authorization form. The use and disclosure of

protected health information will be limited to the individuals described in the Research Authorization form. A Research Authorization form must be completed by the Principal Investigator and approved by the IRB and Privacy Board (IRB/PB).

17.2 Serious Adverse Event (SAE) Reporting

Any SAE must be reported to the IRB/PB as soon as possible but no later than 5 calendar days. The IRB/PB requires a Clinical Research Database (CRDB) SAE report be submitted electronically to the SAE Office at [contact]. The report should contain the following information:

Fields populated from CRDB:

- Subject's name (generate the report with only initials if it will be sent outside of MSKCC)
- Medical record number
- Disease/histology (if applicable)
- Protocol number and title

Data needing to be entered:

- The date the adverse event occurred
- The adverse event
- Relationship of the adverse event to the treatment (drug, device, or intervention)
- If the AE was expected
- The severity of the AE
- The intervention
- Detailed text that includes the following
 - A explanation of how the AE was handled
 - A description of the subject's condition
 - Indication if the subject remains on the study
 - If an amendment will need to be made to the protocol and/or consent form.

The PI's signature and the date it was signed are required on the completed report.

For IND/IDE protocols:

The CRDB AE report should be completed as above and the FDA assigned IND/IDE number written at the top of the report. If appropriate, the report will be forwarded to the FDA by the SAE staff through the IND Office.

17.2.1 Definition of SAEs/Reporting to Novartis and the National Comprehensive Cancer Network (NCCN)

All AEs and SAEs will be collected from the initiation of the study drug until 28 days after discontinuation of the last dose of the study drug. Definitions for adverse events can be found in Section 11. A serious adverse event is defined as any adverse event that:

- Results in death
- Is life-threatening

- Requires hospitalization or prolongation of an existing hospitalization
- Results in disability/incapacity
- Results in congenital anomaly or birth defect
- Any event which requires intervention to prevent the previously stated outcomes

In addition to standard institutional practice and reporting, all SAEs must be reported to Novartis and NCCN within 24 hours. The SAE should be recorded on an MSK CRDB SAE report and after de-identification faxed to the attention of:

- Local Novartis Drug Safety and Epidemiology Safety Desk
 - [contact]
 - Should the designated SAE Fax# be non-functional please send SAEs to the designated SAE mailbox: [contact]
 - Please include Novartis SAE report coversheet for any SAE report

And:

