11.0 TOXICITIES/SIDE EFFECTS

11.1 Adverse Events

An Adverse Event (AE) is any unfavorable and unintended sign, symptom, or disease temporally associated with the use of an investigational medicinal product or other protocol-imposed intervention, regardless of attribution.

This includes the following:

- AEs not previously observed in the patient that emerge during the protocol specified AE reporting period, including signs or symptoms associated with recurrence of melanoma that were not present prior to the AE reporting period.
- Complications that occur during the study as a result of protocol-mandated interventions (e.g., invasive procedures such as biopsies).
- AEs that occur prior to assignment of study treatment that are related to a protocol-mandated intervention (e.g., invasive procedures such as biopsies or medication washouts).
- Preexisting medical conditions that are judged by the investigator to have worsened in severity or frequency or changed in character during the protocol-specified AE reporting period.

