11.2 Serious Adverse Event

Serious Adverse Events (SAEs) as defined by the FDA will be recorded and reported as detailed in section 17.2. Recurrent melanoma will not be considered an SAE. However, development of a new primary melanoma will be reported as a SAE.

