11.3 Assessment of Adverse Events

All adverse events encountered during the study will be evaluated according to the NC I Common Toxicity Grading system version 4.0. Grade, duration and treatment will be recorded. Life threatening toxicities and serious adverse events should be reported immediately to the Principal Investigator.

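### The evaluation that 9.1 requires after cycle 4 is absent from the calendar in 10.1 and Table 8, and the 17.2.1 collection window does not reach all events named in 11.1 and 11.2

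*Combined protocol and SAP*

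**What the plan says.** **Visits.** Section 9.1 has each participant seen in clinic after each cycle, within 5 days either way, for an evaluation whose content it takes from section 10. It also has the pill diary reviewed when each cycle ends. Section 12.3 grades toxicity with each cycle. Section 10.1 places the clinical visits at the start of each cycle, and Table 8 marks history, examination, laboratories, ECG and diary at weeks 1, 5, 9 and 13. (The header rows of Table 8 are displaced in the copy reviewed, but the text of 10.1 gives the same placement.) At the end of cycle 4 the calendar holds imaging and a dermatology examination. The next full visit is at 6 months, with no stated time origin and no ECG or diary.

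**Collection of adverse events.** Section 17.2.1 states: "All AEs and SAEs will be collected from the initiation of the study drug until 28 days after discontinuation" of the last dose. Section 11.1 counts as adverse events "AEs that occur prior to assignment of study treatment that are related to a protocol-mandated intervention" and also "Complications that occur during the study as a result of protocol-mandated interventions (e.g., invasive procedures such as biopsies"). Its other two bullets refer to a reporting period, for example "AEs not previously observed in the patient that emerge during the protocol specified AE reporting period". Section 11.2 says that "development of a new primary melanoma will be reported as a SAE", and more generally that "Serious Adverse Events (SAEs) as defined by the FDA will be recorded and reported as detailed in section 17.2". Section 17.2 adds: "Any SAE must be reported to the IRB/PB as soon as possible but no later than 5 calendar days".

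**The concern.** The visits that open cycles 2, 3 and 4 can double as the visits that close cycles 1, 2 and 3. Nothing in 10.1 or Table 8 does this for cycle 4. The pointer in 9.1 thus leads to a section that does not contain the visit. Sites usually work from the study calendar, so the last cycle's toxicity could be graded without a scheduled history, laboratory panel, ECG or diary review. Toxicity is a secondary objective (2.2).

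The collection window raises a related question. Some events that 11.1 and 11.2 treat as adverse or serious can occur before first dose or well after the window closes. Section 17.2.1 is headed for reporting to the manufacturer and NCCN, while 17.2 sends serious events to the IRB/PB with no end date. A reader cannot tell which reporting the window governs.

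**Working it through.** **Inputs.** Four cycles of 28 days (4.2); visits at weeks 1, 5, 9 and 13, within 5 days (10.1, Table 8); window end 28 days after the last dose (17.2.1); 6-month visit within 2 weeks (10.1); enrolment within 90 days of surgery (6.1.1, 14.0). Assumptions: no treatment delays; one month = 365.25/12 = 30.4375 days; dosing starts *s* days after surgery, with *s* from 0 to 90. The plan gives no figure of its own to reproduce here.

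1. Last dose: 4 × 28 = day 112. Collection closes: 112 + 28 = day 140.
2. Cycles end on days 28, 56, 84 and 112. Visits fall on days 1, 29, 57 and 85. Days 29, 57 and 85 close cycles 1 to 3; no visit follows day 112. Cycle 4 is days 85 to 112, so 28/112 = 25% of planned dosing.
3. From the week 13 visit to closure: 140 − 85 = 55 days, or 55/140 = 39% of the collection period. With the 5-day allowance: 140 − 90 = 50 to 140 − 80 = 60 days (36% to 43%).
4. Month 6 counted from first dose: 6 × 30.4375 ≈ day 183, or 169 to 197 with the allowance. This is 183 − 140 = 43 days after closure (29 to 57). The 55-day gap in step 3 is then uninterrupted on the calendar.
5. Month 6 counted from surgery: it falls 183 − *s* days after first dose. It is inside the window when 183 − *s* ≤ 140, so *s* ≥ 43 (29 if held two weeks early, 57 if two weeks late). It falls on or after the last dose when 183 − *s* ≥ 112, so *s* ≤ 71. At nominal dates it can close cycle 4 within the window for *s* from 43 to 71. For *s* up to 90 it falls as early as day 93, during cycle 4. In all these cases it brings history, examination and laboratories, but no ECG or diary.
6. If 9.1 is followed, a visit occurs at about day 112 and the remaining stretch to closure is 140 − 112 = 28 days.

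**Window against the other sections.**

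- *Before first dose.* Section 8.3 requires contrast brain imaging within 4 weeks (28 days) of the start, and 8.4 requires further imaging and blood tests. Related events meet the third bullet of 11.1 but precede collection.
- *Procedures later in the study.* The second bullet of 11.1 has no treatment-based limit. The relapse biopsy is marked mandatory in Table 8, footnote f, yet 3.5, 10.2 and 17.0 describe it as standard care. Whether its complications qualify is therefore unsettled.
- *New primary melanoma.* Follow-up from closure to 24 months after surgery is 730.5 − *s* − 140, about 590 days (*s* = 0) to 500 days (*s* = 90). Of the seven visits at months 6, 9, 12, 15, 18, 21 and 24, seven (*s* = 0; closure at 4.6 months from surgery) or six (*s* = 90; closure at 7.6 months) fall after closure, counted from surgery.

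**The case against.** Much can be said for the plan. Section 9.1 itself requires the visit and diary review after cycle 4, so the protocol is not silent. The dermatology examination at that point is partly for toxicity, and Appendix C tells patients to bring the diary and unused capsules to each appointment. Surgery is also a natural clock for month 6: the same part of 10.1 ends follow-up 24 months from resection, and recovery from surgery is required first, so later starts are plausible. These arguments stand. They mean that a reader who infers that some 40% of the collection period always lacks a check goes too far. That figure needs both 9.1 to be ignored and month 6 to be counted from first dose. They do not remove the mismatch between 9.1 and the calendar, and none of them supplies an ECG or a scheduled diary review.

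On the window, the first and fourth bullets of 11.1 accept a reporting period, which 17.2.1 supplies, and 11.2 defers to 17.2. Section 11.3 says "All adverse events encountered during the study will be evaluated", but it chiefly sets out how events are graded, so it is weak evidence of a competing window and is not relied on here. A reader might also infer that a late new primary melanoma has no rule at all. The documents do not support that: 11.2 makes it a serious event, 17.2 sets no end date for the IRB/PB, and examinations continue every 3 months. What remains is a reporting duty that outlasts the stated collection period. Part of 17.2.1, after the manufacturer's contact details, was not available and might bear on this.

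**Conclusion.** The point holds as a minor inconsistency. For the calendar, the firm result is that cycle 4, a quarter of planned dosing, has no scheduled closing history, laboratory, ECG or diary check in 10.1 and Table 8, although 9.1 calls for one. The longer gap of about 55 days before collection closes is conditional on month 6 running from first dose. Under a surgical origin, history, examination and laboratories may fall inside the window when dosing starts about 43 or more days after surgery; ECG and diary do not.

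For the window, the visible text leaves out procedure-related events before treatment, complications of protocol-mandated procedures later in the study, and new primary melanoma after about day 140. The documents give no rate for any of these, so the number of events missed is unknown. Toxicity is tabulated without a decision threshold (14.0), and the 24-month relapse-free survival endpoint is unaffected. The day counts assume no treatment delays.

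**What to change.** - Reconcile 10.1 and Table 8 with 9.1, so that text and calendar agree on the evaluation and diary review after cycle 4.
- State whether the 6-month visit is counted from surgery or from first dose.
- In 17.2.1, state whether the 28-day window governs reporting to the IRB/PB as well as to the manufacturer and NCCN.
- Align the window with the second and third bullets of 11.1, and say whether the relapse biopsy is protocol-mandated for this purpose.
- Align it with 11.2 by capturing new primary melanoma at the existing follow-up visits to month 24 or recurrence.

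Capture after relapse would be a new requirement. The six-monthly chart review in 10.1 is described for patients still free of disease after 24 months and is limited to survival status, and section 13 lists recurrence as a reason for removal from study.

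The cost is wording in three places, a few additional adverse event entries, and one calendar entry that 9.1 already requires, in 23 patients. The 28-day window for general adverse events can stay.

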18.0 INFORMED CONSENT PROCEDURES

Before protocol-specified procedures are carried out, consenting professionals will explain full details of the protocol and study procedures as well as the risks involved to participants prior to their inclusion in the study. Participants will also be informed that they are free to withdraw from the study at any time. All participants must sign an IRB/PB-approved consent form indicating their consent to participate. This consent form meets the requirements of the Code of Federal Regulations and the Institutional Review Board/Privacy Board of this Center. The consent form will include the following:

1. The nature and objectives, potential risks and benefits of the intended study.
2. The length of study and the likely follow-up required.
3. Alternatives to the proposed study. (This will include available standard and investigational therapies. In addition, patients will be offered an option of supportive care for therapeutic studies.)
4. The name of the investigator(s) responsible for the protocol.
5. The right of the participant to accept or refuse study interventions/interactions and to withdraw from participation at any time.

Before any protocol-specific procedures can be carried out, the consenting professional will fully explain the aspects of patient privacy concerning research specific information. In addition to signing the IRB Informed Consent, all patients must agree to the Research Authorization component of the informed consent form.

Each participant and consenting professional will sign the consent form. The participant must receive a copy of the signed informed consent form.

20.0 APPENDICES

Appendix A: ECOG/KPS Conversion Table

Appendix B: Prohibited and Cautionary Medications

Appendix C: Pill Diary

Appendix A: ECOG/KPS Conversion Table

ECOG Performance Status Scale		Karnofsky Performance Scale	
Grade	Description	Percent	Description
0	Normal activity. Fully active, able to carry on all pre-disease performance without restriction.	100	Normal, no complaints, no evidence of disease.
		90	Able to carry on normal activity; minor signs or symptoms of disease.
1	Symptoms, but ambulatory. Restricted in physically strenuous activity, but ambulatory and able to carry out work of a light or sedentary nature (e.g., light housework, office work).	80	Normal activity with effort, some signs or symptoms of disease.
		70	Cares for self, unable to carry on normal activity or to do active work.
2	In bed <50% of the time. Ambulatory and capable of all self-care, but unable to carry out any work activities. Up and about more than 50% of waking hours.	60	Requires occasional assistance, but is able to care for most of his/her needs.
		50	Requires considerable assistance and frequent medical care.
3	In bed >50% of the time. Capable of only limited self-care, confined to bed or chair more than 50% of waking hours.	40	Disabled, requires special care and assistance.
		30	Severely disabled, hospitalization indicated. Death not imminent.
4	100% bedridden. Completely disabled. Cannot carry on any self-care. Totally confined to bed or chair.	20	Very sick, hospitalization indicated. Death not imminent.
		10	Moribund, fatal processes progressing rapidly.
	Dead.		Dead.

5		0	
---	--	---	--

APPENDIX B: Prohibited and Cautionary Medications

PROHIBITED MEDICATIONS	
Strong CYP2C8/3A/PGP/BCRP1 Inhibitor/Inducer. May alter levels of DABRAFENIB	Therapeutic Area
Clarithromycin, telithromycin, rifamycin class agents (e.g. rifampin, rifabutin, rifapentine), toleandomycin	Antibiotics
Itracozazole, ketoconazole, posaconazole, voriconazole	Antifungals
Nefazodone	Antidepressants
Gemfibrozil	Hyperlipidemia
Carbamazepine, phenobarbital, amiodarone, phenytoin, s-mephenytoin, bosentan, mibefradil, conivaptan	Miscellaneous
Cyclosporine	Immunosuppressive agents

CAUTIONARY MEDICATIONS	
CYP2C8/C9/C19 Substrates; these drugs may be altered (increased or decreased) by DABRAFENIB	Therapeutic Area
Cerivastatin	HMG-CoA Reductase Inhibitors
Tolbutamide, nateglinide, repaglinide	Antidiabetics
Amitriptyline, clomipramine, imipramine	Antidepressants
Mild/Moderate Inhibitor of CYP3A, CYP2C8, PGP and BCRP1; These drugs may increase concentrations of DABRAFENIB	
	Therapeutic Area
Erythromycin	Antibiotic
Fluconazole	Antifungal

Diltiazem, verapamil	Antiarrhythmics
Aprepitant, cimetidine, montelukast	Miscellaneous
Substrates of CYP3A4/CYP2B6/CYP2C8/CYP2C9/CYP2C19 that may be affected by induction by DABRAFENIB; These drugs may lose efficacy when co-administered with DABRAFENIB	
Therapeutic Area	
Chloramphenicol, doxycycline, erythromycin, moxifloxacin	Antibiotics
Caspofungin, fluconazole, terbinafine	Antifungals
Amlodipine, diltiazem, felodipine, nifedipine, nilvadipine, nisoldipine, verapamil	Antihypertensives
Aripiprazole, bupropion, buspirone, desipramine, haloperidol, mirtazapine, pimozide, quetiapine, trazodone	Antidepressants and Antipsychotics
Glyburide, saxagliptin, tolbutamide	Antidiabetics
Lamotrigine, valproate, divalproex, zonisamide,	Anticonvulsants
Alfentanil, buprenorphine, celecoxib, codeine, fentanyl, methadone, oxycodone	Analgesics
Aprepitant, cisapride, darifenacin, disopyramide, leflunomide, methohexital, oral contraceptives, quinine, ranitidine, sulfenacin, sulfasalazine, tramadol, tolvaptan	Miscellaneous
Alprazolam, brotizolam, diazepam, estazolam, midazolam, triazolam, zolpidem, zopiclone	Hypnotics and Sedatives
Diergotamine, ergotamine, eletriptan	Antimigraine agents
Everolimus, sirolimus, tacrolimus	Immunosuppressive agents
Astemizole, chlorpheniramine, ebastine	Antihistamine
Oral budesonide, methylprednisolone	Corticosteroids
Sildenafil, tadalafil, vardenafil	Erectile Dysfunction agents
Eplerenone	Selective Aldosterone Blockers
Disopyramide, dronedarone, mexiletine, propafenone, quinidine	Antiarrhythmics
Lovastatin, atorvastatin, simvastatin	HMG-CoA Reductase Inhibitors
Cilostazole, warfarin	Anticoagulants and Antiplatelets
Ritonavir, nevirapine, efavirenz, zidovudine	Antiretrovirals

